9.1.3 Exploratory Estimands

The exploratory objectives described in Section 0 do not relate to estimating or defining the magnitude of the treatment effect, hence the construction of exploratory estimands is not applicable.

9.2 Population Sets

```
9.2.1 All Enrolled Analysis Set
```

The all enrolled analysis set (ENRL) consists of all patients who signed informed consent for this study.

9.2.2 All Randomised Analysis Set

The all randomised analysis set consists of all patients who were randomised into the study. Patients will be summarised by the treatment group they were randomised to.

9.2.3 Full Analysis Set

The Full Analysis Set (FAS) will include all randomised patients who receive at least one full dose of IMP (i.e. 800mg or two tablets). Patients will be analysed according to randomised treatment regardless of the treatment they actually received. This analysis set will be the primary set used for all efficacy analyses.

9.2.4 Per-Protocol Analysis Set

The PPS will include all patients in the FAS who complied sufficiently with the protocol with respect to exposure to IMP, availability of tumour assessments, and absence of important protocol deviations likely to impact efficacy outcomes. This will be identified via the Protocol Deviation Log, where a patient with any deviation categorised as "Y" for the flag "Impact to Primary Endpoint (Y/ N)" will be excluded.

Patients will be analysed based on the treatment group they were randomised to regardless of the actual treatment received.

9.2.5 Safety Analysis Set

The Safety Analysis Set will include all randomised patients who receive at least one tablet of IMP. Patients will be analysed according to treatment they actually received. This analysis set will be used for summaries of safety data.

9.2.6 Pharmacokinetics Analysis Set

The PK Analysis Set will include all patients who receive at least one dose of setanaxib and have at least one measured concentration, including any BQL, at a scheduled PK time point post-dose. Patients will be analysed according to treatment they actually received.

10.0 Conventions and Derivations

10.1 Baseline, Change and Percent Change from Baseline

Baseline is defined as the last non-missing value before the first dose of IMP. Baseline values will generally be assessed at the Day 1 visit, the exception to this is the Initial tumour imaging scan which will be performed within 35 days prior to the date of treatment and will be used as the Baseline scan for the tumour assessments. For re-screened patients, the value associated with their screen failure record will not be considered for baseline.

If time of assessment is not collected and the assessment is collected on the same date as the first dose, the assessment will be assumed to be per protocol, i.e. prior to first dose. If multiple continuous assessments occur on the same day as first dose and no time is recorded, the average value will be used as baseline.

Change from baseline at any post-baseline time point will be defined as:

- Absolute Change from Baseline = (Value at Post Baseline Time Point Value at Baseline)
- Ratio of Postbaseline to Baseline = $\left(\frac{Value \ at \ Post \ Baseline \ Time \ Point}{Value \ at \ Baseline}\right)$

Percentage change from baseline at any post-baseline time point will be defined as:

• Percentage Change from Baseline = $100 * \left(\frac{Value \ at \ Post \ Baseline \ Time \ Point-Value \ at \ Baseline}{Value \ at \ Baseline}\right)$

10.2 Study Day and Durations

The reference start date for safety and PK assessments will be the start date of IMP, whilst for all efficacy assessments it will be the date of randomisation.

Study Day is calculated as follows. Where (Prior) indicates the date of assessment if before the reference start date, and (Post) indicates it is on or after:

- Study Day (Prior) = (Date of Assessment Reference Start Date)
- Study Day (Post) = (Date of Assessment Reference Start Date)+1

Whilst Section 10.13 details the imputation of partial dates, the duration of any event involving partial or missing dates will not be calculated. Otherwise where the duration of an event or the time since an event, is to be presented in days, the calculation is given as;

• Duration (days) = (End Date - Start Date)+1

If a duration is required to be presented in a different time unit, the appropriate conversions are given below;

- Duration (Years) = $\left(\frac{Duration(days)}{365.25}\right)$
- Duration (Months) = $\left(\frac{Duration(days)}{30.4375}\right)$
- Duration (Weeks) = $\left(\frac{Duration(days)}{7}\right)$

10.3 Screening Failures

Screening failures are patients who have signed informed consent and failed screening criteria in the study. These patients will not be enrolled into the treatment phase.

10.4 Visit Windowing

For the purposes of the analysis, observations will be assigned to analysis visits using the windows detailed in Table 1. All visits (including unscheduled, EoT and safety follow-up visits) will be windowed to the appropriate analysis visit regardless of the visit label entered in the eCRF. Safety follow-up visits will only contribute to the Safety follow-up analysis visit. Tabulations will only summarise scheduled time points for the assessments.

If more than one quantitative measurement falls within a post baseline visit window, then the following rules will apply;

- For PK assessments, the latest value on or prior to the day of IMP administration within a given window will be selected. If there is more than one record on the selected day, then;
 - For Analysis Visit Week 9, the arithmetic mean of the assessments will be calculated.
 - For all other Analysis Visits, the latest pre-dose assessment will be used.
- For all other assessments, the value closest to the target day will be selected. If more than one assessment is equidistant from the target day, the assessment later in time will be selected. If more than one record remains, then the arithmetic mean of the assessments will be calculated.
 - ECG assessments are scheduled to be collected at pre-dose and post-dose timepoints on Study Day 1 and 22. Where multiple assessments occur on the same day in these instances, the timepoint will be preserved.
- If the EoT assessment and a scheduled assessment reside within the same visit window, the scheduled assessment will be selected.

If more than one quantitative measurement meets the Baseline definition (Section 10.1), then then the arithmetic mean of the assessments will be calculated.

If more than one qualitative measurement falls within a baseline or post-baseline visit window, then a conservative approach will be taken by selecting the worst result.

Analysis Visit	Target	Window for Safety	Window for Efficacy
Analysis Visit	Study Day		(Tumour Biopsies / Assessments)
Baseline	1		
Day 1	1		
Week 3	22	(±5)	
Week 6	43	(±5)	
Week 9	64	(±5)	(±7)
Week 12	85	(±5)	
Week 15	106	(±5)	(±7)
Week 18	127	(±5)	
Week 21	148	(±5)	(±7)
Week 24	169	(±5)	
Week 27	190	(±5)	(±7)
Week 30	211	(±5)	
Week 33	232	(±5)	(±7)
Week 36	253	(±5)	
Week 39	272	(±5)	(±7)
Week 42	295	(±5)	
Week 45	316	(±5)	(±7)
Week 48	337	(±5)	
Week 51	358	(±5)	(±7)
Week 54	379	(±5)	
Week 57	400	(±5)	(±7)
Week 60	421	(±5)	
Week 63	442	(±5)	(±7)
Week 66	463	(±5)	
Week 69	484	(±5)	(±7)
Week 72	505	(±5)	
Week 75	526	(±5)	(±7)
Week 78	547	(±5)	
Week 81	568	(±5)	(±7)

Table 1.Analysis Visit Windows

Week 84	589	(±5)	
Week 87	610	(±5)	(±7)
Week 90	631	(±5)	
Week 93	652	(±5)	(±7)
Week 96	673	(±5)	
Week 99	694	(±5)	(±7)
Week 102	715	(±5)	
Week 105	736	(±3)	(±7)
Safety Follow-Up	EoT+28 days	(±7)	

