6.0 Introduction

This SAP should be read in conjunction with the study protocol and electronic case report form (eCRF). This version of the SAP has been developed by ICON using protocol version v5.0 dated 12 December 2023 along with the local amendment for the United Kingdom (v4.2 dated 25 April 2023) and CRF v5.0 dated 19 September 2023. Any further changes to the protocol or eCRF that have an impact on the design or the planned statistical analysis will require updates to the SAP.

The initial version of the SAP will be signed prior to the biomarker interim analysis (see Section 11.0 for details). The final version of the SAP, will be issued for sponsor approval prior to the data cut off for the updated analysis (see Section 8.4 for details on the timing of database lock).

A separate Independent Data Monitoring Committee (IDMC) SAP (v1.0 dated 16 December 2022) documents the details of the regular safety and tolerability reviews performed by an unblinded IDMC.

The full set of tables, listings and figures (TLFs) described in this SAP will be produced for the primary analysis and the updated analysis. If there are patients continuing in the study after the updated analysis, a small set of adverse events (AEs), serious adverse events (SAEs) and other selected safety data listings will be updated and included in an addendum to the CSR. The full set of outputs will not be reproduced.

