8.0 Study Design

This is a randomised, double-blind, placebo-controlled, proof-of-concept, Phase 2 study assessing setanaxib coadministered with pembrolizumab in patients with recurrent or metastatic SCCHN. The safety and efficacy of setanaxib 800 mg BID will be assessed against matching placebo over up to 105 weeks of treatment. The design is depicted in Figure 1.

AE=adverse event; CAFs=cancer-associated fibroblasts; IV=intravenously; PFS=progression-free survival; PO=per os (orally, or via either a feeding tube or a percutaneous endoscopic gastrostomy device in case patients are unable to swallow tablets); q3w=every 3 weeks; R=randomisation; RECIST v1.1=response evaluation criteria in solid tumours version 1.1 * For patients with a suitable archival tumour biopsy sample available, the archival sample may be used to assess CAFs level and determine eligibility (Note: this can only be performed after the patient has provided signed informed consent). This will not dispense from the need for a recent pre-study tumour biopsy.

The study plans to randomise approximately 50 patients at up to approximately 35 investigational centres in North America and Europe, to the IMP, according to a 1:1 randomisation ratio, stratified by HPV status. Depending on the number of patients providing evaluable Week 9 biopsy and imaging data, up to an additional 20 patients (making a maximum of 70 patients) may be randomised to ensure an adequate amount of data is available for the efficacy and biomarker analyses.

The study will consist of an up to 35-day Screening Period, an up to 24-month Treatment Period (Day 1 to Week 105), and a 28-day Safety Follow-up Period. The total duration of the study for patients remaining in the study until their final follow-up assessment will be up to approximately 114 weeks (approximately 2 years and 2 months).

All patients included in this study will receive pembrolizumab, with setanaxib or placebo given as add-on therapy to a recognised and approved standard-of-care agent.

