10.9 Disease Response

10.9.1 Overall Visit Response

The first on study imaging assessment should be performed at Visit 5 (Week 9 ± 1 week), and then every 6 weeks (± 1 week) through the first year, and every 9 weeks (± 1 week) thereafter for up to 24 months. Tumour assessments will be conducted from the date of randomisation and continue until PD, irrespective of treatment discontinuation.

RECIST v1.1 will be used to determine each patient's overall visit response according to target lesions, non-target lesions (NTLs) and new lesions (Table 3). The overall visit responses are recorded on the Disease Response page of the eCRF, however these will be programmatically re-derived based on the target response, non-target response, and new lesion indicator, also collected on the Disease Response page of the eCRF for each visit. The derived overall visit response will be used in the analysis of secondary endpoints.

TLs	NTLs	New Lesions	Overall Visit Response
CR	CR	No	CR
CR	Non-CR / Non-PD	No	PR
CR	NE	No	PR
PR	Non-PD / NE	No	PR
SD	Non-PD / NE	No	SD
NE	Non-PD	No	NE
PD	Any	Yes / No	PD
Any	PD	Yes / No	PD
Any	Any	Yes	PD

Table 3.Overall Visit Response

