12.5 Efficacy Analyses

The data cut-off for the primary analysis will occur approximately 15 weeks after completion of enrolment, when all patients are expected to have had at least 5 cycles of pembrolizumab, at least two post-treatment scans, and the opportunity for a post-treatment tumour biopsy. This analysis will include the primary endpoint of best percentage change in tumour size and all secondary endpoints (excluding Cox proportional hazards for PFS) will be analysed. Investigators and patients will continue to be blinded to randomised study treatment after initial unblinding of data for the primary analysis until the final database lock.

An updated analysis may be performed after approximately 38 progression events have been reported. This updated analysis will include only the secondary endpoints of PFS, and OS in addition to an updated waterfall plot for the primary endpoint of best percentage change in tumour size.

During ongoing review of the overall progression event count, if the predicted timing of the initial and updated analyses are expected to be close in proximity, one analysis may be performed.

Efficacy analyses will be conducted using the FAS. To understand the robustness of the results from important protocol deviations, the primary efficacy analyses will also be performed using the PPS.

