12.5.2 Primary Estimand

The primary estimand attributes are given in Section 9.1. All analysis visits will be summarised using univariate statistics and a waterfall plot for the best percentage change from baseline will also be presented.

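### SAP Table 1 keeps 6-weekly tumour windows after year 1 although scans become 9-weekly, so 3 of 6 year-2 scans fit no window; the Week 39 target day is also wrong (272 for 274)

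*SAP*

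**What the plan says.** SAP 10.4 states that "observations will be assigned to analysis visits using the windows detailed in Table 1", whatever visit label stands in the eCRF. In Table 1 the efficacy column (biopsies and tumour assessments) has a ±7-day window at Weeks 9, 15, 21 and so on in 6-week steps to Week 105. The rows for Weeks 60, 78 and 96 carry a safety window only. Week 39 has target Day 272.

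SAP 10.9.1 gives the scan calendar. It begins "The first on study imaging assessment should be performed at Visit 5", which is Week 9 ±1 week. Scans are then 6-weekly "through the first year, and every 9 weeks" thereafter, each ±1 week, for up to 24 months. Protocol 5.2.1.2 says the same. SAP 8.0 describes "an up to 24-month Treatment Period (Day 1 to Week 105"). SAP 10.2 sets Day 1 as the first IMP dose for safety, "whilst for all efficacy assessments it will be the date of randomisation".

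On use of the windows, SAP 12.5.2 says "All analysis visits will be summarised using univariate statistics". On timing, SAP 6.0 says the full set of outputs "will be produced for the primary analysis and the updated analysis", whereas SAP 12.5 says "This updated analysis will include only the secondary endpoints of PFS, and OS", plus an updated waterfall plot.

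**The concern.** Table 1 does not change at the end of year 1, when the scan interval does. A scan done exactly on schedule in year 2 can therefore land between two efficacy windows and belong to no analysis visit. Nothing else in the SAP clearly recovers it. The eCRF label is overridden, there is no nearest-visit rule for a value outside every window, SAP 10.4 limits tabulations to scheduled time points, and SAP 12.0 sends unscheduled values to listings except in worst-result assessments. The Week 39 row is a separate slip that shifts one window two days early, for safety data as well as scans.

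At stake are the by-visit summaries of tumour size and some Week 39 safety values. A programmer following the table literally would drop protocol-compliant data from them and tabulate visits at which no scan is due.

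**Working it through.** **Target-day rule.** With Day 1 as the reference date, the target for Week w is 7w + 1. SAP 10.4 uses this convention itself when it places the second paired ECG day on Study Day 22 (7×3 + 1, Week 3). The rule reproduces 34 of the 35 weekly rows in Table 1. The exception is Week 39: 7×39 + 1 = 274, printed 272. Its neighbours are 253 (Week 36) and 295 (Week 42), and 253 + 21 = 274.

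**Anchor for the 9-weekly phase.** The SAP does not name it. Week 51 is the natural choice: it is the last 6-weekly scan within 52 weeks, and 51 + 6×9 = 105, the end of the treatment period.

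**Permitted scan days.** These are (7w + 1) ± 7, or 15 days per scan, compared with each Table 1 efficacy target ±7.

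| Year-2 scan (Week 51 anchor) | Permitted days | Nearest efficacy windows | Days covered |
|---|---|---|---|
| Week 60 | 414–428 | 393–407 and 435–449 | 0 of 15 |
| Week 69 | 477–491 | 477–491 | 15 of 15 |
| Week 78 | 540–554 | 519–533 and 561–575 | 0 of 15 |
| Week 87 | 603–617 | 603–617 | 15 of 15 |
| Week 96 | 666–680 | 645–659 and 687–701 | 0 of 15 |
| Week 105 | 729–743 | 729–743 | 15 of 15 |

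Uncovered: 3×15 = 45 of 6×15 = 90 permitted days. Conversely, 6 of the 9 year-2 windows (Weeks 57, 63, 75, 81, 93 and 99) have no scheduled scan.

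**Other anchors.**

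- Week 57 anchor: year-2 scans fall at Weeks 57, 66, 75, 84, 93 and 102. Weeks 66 (456–470), 84 (582–596) and 102 (708–722) lie wholly inside the gaps 450–476, 576–602 and 702–728. Again 3 of 6 scans and 45 of 90 days are uncovered, with Week 57 itself counted as a year-2 scan.
- Week 45 anchor: Weeks 54, 72 and 90 are wholly uncovered.

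**Week 39.**

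- Scans: permitted 267–281, printed window 265–279, so Days 280–281 are uncovered (2 of 15).
- Safety (±5 days, from the protocol's Schedule of Assessments): permitted 269–279, printed window 267–277, so Days 278–279 are uncovered (2 of 11).
- No other year-1 scan week, and no other safety week from 3 to 102, has an uncovered permitted day.

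**Who could be affected at the primary cut-off.** The cut-off is about 15 weeks after enrolment closes (SAP 12.5).

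- Week 60: the earliest permitted scan, Day 414, is (414 − 1)/7 = 59 weeks after randomisation, so the patient must have been randomised at least 59 − 15 = 44 weeks before closure.
- Week 78: Day 540 gives 77 − 15 = 62 weeks.
- Week 96: Day 666 gives 95 − 15 = 80 weeks.

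The documents give no enrolment dates, so the number of affected patients cannot be computed.

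**The case against.** The strongest argument is that the practical consequence is close to nil. SAP 12.5 confines the updated efficacy analysis to PFS, OS and a waterfall plot, so by-visit tumour tables may be run only at the primary cut-off, when few patients will have year-2 scans. Protocol 3.2 expects only about 8 of 25 setanaxib patients to be on treatment for 12 months or more. Presentation detail also sits in table shells that are not in the documents. This stands as a limit on importance. It does not remove the contradiction, and SAP 6.0, which promises the full output set at both analyses, points the other way.

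The counts also depend on conventions. Counting only scans after a Week 57 anchor gives 3 of 5 rather than 3 of 6, with the same three scans lost. The protocol's Schedule of Assessments prints Week 105 as Day 735 (7×105), where the SAP prints 736. On a 7w count, Week 39 would be Day 273, and only one scan day (280) and one safety day (278) would be uncovered. SAP Table 1 plainly follows 7w + 1, however. The 272 was also read from extracted PDF text, so a glance at the source is sensible.

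Finally, the PFS censoring rule in SAP 10.8.1 refers to two consecutive missed visits without defining them. The rule does not cite Table 1, so no effect on PFS is shown. A clarification would still help: if Table 1 windows were used to count missed visits, Weeks 57 and 63 would both look missed before an on-schedule Week 69 scan.

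**Conclusion.** The concern holds and is minor. Table 1 contradicts the SAP's own scan schedule after year 1. Under either a Week 51 or a Week 57 anchor, 3 of 6 year-2 scans (45 of 90 permitted days) fit no efficacy window. The Week 39 target is two days early by the table's own rule.

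The effect is confined to by-visit descriptive summaries. The definitions of best percentage change, BOR, ORR, DCR, DoR, PFS and OS (SAP 10.7.6 to 10.9.5) do not refer to the windows, so the primary ANCOVA and the time-to-event analyses do not change. The year-2 result assumes scans done on schedule within ±1 week. The Week 39 counts assume the 7w + 1 day count.

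**What to change.** 1. State in SAP 10.9.1 or 10.4 which scan the 9-weekly phase counts from. This must come first, because rows built for a Week 51 anchor would leave all 6 year-2 scans (90 of 90 days) uncovered if the anchor were Week 57.
2. If the anchor is Week 51, replace the efficacy windows after Week 51 with Weeks 60, 69, 78, 87, 96 and 105 (Days 421, 484, 547, 610, 673 and 736, each ±7). All 90 permitted days are then covered. If the anchor is another scan, derive the rows from that scan.
3. Correct the Week 39 target to Day 274, which gives an efficacy window of 267–281 and a safety window of 269–279.

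Two optional clarifications, neither of them an error shown here: say that missed visits in SAP 10.8.1 means missed scheduled tumour assessments, and confirm that a progression biopsy taken before Day 57 (the start of the Week 9 window, 64 − 7) counts as the on-treatment biopsy.

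The cost is one sentence, a few table rows and minor reprogramming of the windows after the dry run. No extra data are needed.

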- ^h Blood samples (20 mL whole blood) will be collected for analysis of exploratory circulating biomarkers before commencing study treatment, during treatment (at Week 9) and at progression.
- ⁱ Qualitative tests will be performed using urine dipsticks.
- ^j Urine pregnancy test, for females of childbearing potential only, will be performed at each visit before dosing.

Table 1Schedule of Assessments

Study Period	Screening		Double-blind Treatment Period		EoTª	Follow-up ^a	
Study Weeks:	-5 to -1	BL	3, 6, 9, 12, 15, 18, 21, 24, 27, 30, 33, 36, 39, 42, 45, 48, 51, 54, 57, 60, 63, 66, 69, 72, 75, 78, 81, 84, 87, 90, 93, 96, 99, 102	105	EoT Visit	Last IMP Dose+28 (±7 days)	Refer to Footnote 'L' ¹
Study Days (Visit Window):	-35 to -1	1	Every 21 days (±5)	735 (±3)			
Visit:	1	2	3 to 36	37	ЕоТ	Safety Follow-up	Efficacy Follow-up

^k A fresh tumour biopsy will be taken during or within 30 days prior to the Screening Period for assessment of tumour biomarkers (CAFs, CD8⁺ TILs, regulatory T-cells, and PD1-L1) and gene expression analysis. A second biopsy of tumour for assessment of tumour biomarkers and gene expression analysis will be performed 9 weeks (±1 week) after the start of study treatment, or earlier if progression occurs before 9 weeks. A third optional tumour biopsy can be performed at disease progression (only for patients who had their second biopsy at 9 weeks, and who consented to having a third sample).

¹ Tumour response will be assessed on CT/MRI scan using RECIST v1.1 at Visit 5 (Week 9 ±1 week), and then every 6 weeks (±1 week) through the first year, and every 9 weeks (±1 week) thereafter until RECIST v1.1-defined disease progression.

^m Tumour assessments will be conducted from the date of randomisation and continue until RECIST v1.1-defined disease progression, irrespective of treatment discontinuation.

ⁿ Survival will be followed until at least 38 progression events.

^o Pembrolizumab 200 mg will be administered intravenously every 3 weeks

^p Setanaxib 800 mg BID or matching placebo will be administered orally (or via either a feeding tube or a percutaneous endoscopic gastrostomy device in case patients are unable to swallow tablets).

^q Prior medication will be recorded during Screening only.

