Tumour sample may be from either a surgical resection or core needle biopsy or collected as an excisional or incisional tumour biopsy from either the primary or metastatic site during surgery or interventional procedure. Fine needle aspirates are not acceptable. Formalin-fixed paraffin-embedded needle core biopsies may have been obtained via direct visualisation of tumour, or with CT, fluoroscopy, or ultrasound image guided needle biopsy procedures. The tissue cores should have been obtained by the use of an 18 gauge (or larger core diameter) biopsy needle. If smaller needle is used, then additional biopsy cores are to be provided in the block. 10% Neutral buffered formalin is recommended as the tissue fixative.

Samples meeting any of the criteria below are not acceptable:

- Archived tissue with limited tumour content: preferably at least 30% of viable tumour cells
- Cytology samples and fine needle aspirates
- Tissues fixed with other unacceptable fixatives, including 95% alcohol, alcohol formalin acetic acid, and PREFERTM
- Specimens from bone lesions are generally not acceptable unless there is significant soft tissue component or there is no bone tissue in the biopsy

The second biopsy (mandatory for all patients) will be performed 9 weeks (± 1 week) after the start of study treatment or earlier if progression occurs before 9 weeks.

A third optional tumour biopsy can be performed at disease progression (only for patients who had their second biopsy at 9 weeks, who consented to having a third sample).

CAFs will identified in formalin-fixed, paraffin-embedded tissue sections using immunohistochemistry for α SMA. CAFs are positive for α -SMA, and tumour stroma will be assessed for CAFs as previously described (Marsh et al 2011). SMA staining and evaluation of CAF scores will be performed by a single pathologist (or a suitably qualified and trained deputising pathologist) at a central laboratory. The semi-quantitative scoring system separates tumours into 3 groups: low (<5% stroma positive), moderate (5 to 50% stroma positive) and high (>50% stroma positive). Patients with tumours containing moderate or high levels of CAFs will be eligible for the study. The tumour samples will be used for analyses of biomarkers related to SCCHN. The biomarker analyses results will be used to explore the potential relationship with setanaxib response and/or disease progression data obtained in this study.

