12.0 Statistical Methods

With the exception of the unblinded statistician and programmers supporting the IDMC, all personnel involved with the analysis of the study will remain blinded until the initial database soft lock at the time of the primary analysis. Further details on the blinding and unblinding are given in the study Blinding Plan.

In this study, it is planned to recruit approximately 35 investigational centres in USA and Europe. Unless specified otherwise, data from all participating sites will be combined for the analysis, so that an adequate number of patients will be available for analysis. In the event that a single site enrols a large proportion of patients, a site effect may be explored as described in Section 12.5.5, otherwise no site effect will be assessed.

All table summaries will be presented by treatment group (including an overall group for safety tables) and by analysis visit where appropriate. Unscheduled visits will be windowed as described in Section 10.4. Unscheduled visit values will contribute to any assessment of worst/most severe results, but otherwise will only be displayed in listings. Additional details related to specific presentations are given in programming notes of the supporting TFL shells.

Categorical variables will be summarised descriptively using counts and percentages. Percentages will be rounded to one decimal place, except 100%, which will be displayed without any decimal places and percentages will not be displayed for zero counts.

Continuous variables will be summarised using univariate statistics, including the number of observations (n), mean, standard deviation, median, minimum and maximum. The minimum and maximum values will be displayed to the same level of precision as the raw data, the mean and median to a further decimal place and the standard deviation to two additional decimal places. In addition, for tumour and biomarker summaries, the geometric mean and the interval of (geometric mean +/- geometric standard deviation) may also be presented.

Analyses will be performed using SAS® (SAS Institute, Cary, NC, US) version 9.4 or higher.

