12.5.3.2 Change from Baseline in CAFs Level in Tumour Tissue

For the key secondary endpoint of CAFs level, (also referred to as smooth muscle actin [SMA]), it is hypothesised based on the mode of action of setanaxib that there will be a reduction in CAFs level. Data for patients with both baseline and postbaseline results, will be summarised using univariate statistics and will be graphically presented using both boxplots and spaghetti plots for each treatment group.

This secondary efficacy analysis will evaluate the effect of setanaxib on the ratio of postbaseline to baseline CAFs level using an ANCOVA model, including the same covariates as described for the primary analysis in Section 12.5.2.2. Zero values will be replaced as described in Section 12.5.2.1.

A summary of the qualitative CAFs level (in order of increasing severity: Negative, Low Positive, Moderate Positive, Strong Positive) will also be provided.

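### SAP visit windows give no analysis visit to a second biopsy brought forward for progression before Day 57, so the biomarker analyses may leave it out, contrary to the SAP's own estimand

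*SAP*

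**What the plan says.** **Biopsy schedule.** Protocol 5.2.2: "The second biopsy (mandatory for all patients) will be performed 9 weeks" (one week either side) "after the start of study treatment or earlier if progression occurs before 9 weeks". An optional third biopsy at progression is open "only for patients who had their second biopsy at 9 weeks" and who agree to it (also Table 1, footnote k).

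**Windowing.** SAP 10.4: "observations will be assigned to analysis visits using the windows detailed in Table 1", whatever visit label the eCRF carries. In the column of SAP Table 1 that covers tumour biopsies and assessments, the first post-baseline entry is Week 9, Day 64 ± 7, and the next is Week 15, Day 106 ± 7. SAP 10.4 adds: "Tabulations will only summarise scheduled time points for the assessments". SAP 12.0 lets unscheduled values feed assessments of the worst result, "but otherwise will only be displayed in listings". On the reference date for study days, SAP 10.2 says "whilst for all efficacy assessments it will be the date of randomisation".

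**Analysis.** SAP 12.5.3.2, on CAFs: "Data for patients with both baseline and postbaseline results, will be summarised using univariate statistics". The ANCOVA response is the postbaseline-to-baseline ratio, and no analysis visit is named. Sections 12.5.3.3 (CD8+, FOXP3) and 12.5.4.4 (PD-L1) repeat this method.

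**Estimand.** SAP 9.1.2 gives these biomarkers a treatment policy strategy, so values count whether or not an intercurrent event has occurred. Attributes not restated there carry over from the primary estimand in 9.1.1, whose intercurrent events include progression or death.

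**The concern.** The SAP window reproduces the protocol's one-week tolerance around Week 9 but not the clause that moves the biopsy forward on early progression. A mandatory sample taken under that clause before Day 57 therefore belongs to no analysis visit. A programmer following 10.4 and 12.0 to the letter would list it and not analyse it.

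The SAP uses CAFs, CD8+ TILs and regulatory T-cells, together with gene expression, to determine proof of concept (8.1). If early biopsies are left out, patients leave the comparison because of something that happened after randomisation. The plan powers PFS on a hazard ratio of 0.5, so it expects treatment to affect progression. Removal could then be unequal between arms, and the mechanistic contrast would no longer be protected by randomisation. That is a possible bias as well as a loss of precision.

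**Working it through.** **1. The windows.** Week 9 is 64 − 7 = Day 57 to 64 + 7 = Day 71. The protocol's 8 to 10 weeks after Day 1 is 1 + 56 = Day 57 to 1 + 70 = Day 71. The two agree, and the different origins (randomisation in the SAP, start of treatment in the protocol) do no harm because both are planned for Day 1. Week 15 is 106 − 7 = Day 99 to 106 + 7 = Day 113. Days 2 to 56 and Days 72 to 98 have no window for biopsies. A biopsy on Days 72 to 98 is outside the protocol's tolerance. One on Days 2 to 56 after progression is what the protocol asks for.

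**2. The two readings side by side.**

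| Reading | Second biopsy before Day 57 | Optional third biopsy at progression |
|---|---|---|
| Windows applied strictly (SAP 10.4, 12.0) | No analysis visit, listed only | Takes a later visit if it falls in a window from Week 15 on |
| Any postbaseline result (SAP 12.5.3.2, 9.1.2) | Included | Also qualifies, with no rule for choosing between it and the Week 9 sample |

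The 10.4 rule that picks the value nearest the target day works only within one window, so it does not choose between a Week 9 and a later sample. The populations do not settle it either. Protocol 8.2 defines a Biomarker Analysis Set with no timing limit, but SAP 9.2 has no such set.

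**3. Size.** The documents give no rate of progression before Day 57, so there is no plan figure to reproduce. The nearest input is in Protocol 3.2: about 20 of the 25 setanaxib patients (80%) are expected to be treated for at least 3 months.

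- Assumption: constant hazard of stopping, so the share still on treatment at t months is 0.8^(t/3).
- Day 57 in months, with the SAP 10.2 conversion: 57 / 30.4375 = 1.873.
- Off treatment by then: 1 − 0.8^(1.873/3) = 1 − 0.8^0.624 = 1 − 0.870 = 0.130, or 13%.
- Patients: 25 × 0.130 = 3.25, about 3.
- Without the constant-hazard assumption, the share off treatment by Day 57 cannot exceed the 3-month share: 1 − 0.80 = 20%, or 5 of 25.

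Several features make the count of affected biopsies smaller than this:

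- Stopping covers toxicity, withdrawal and death as well as progression.
- The first scheduled scan is at Week 9 (Protocol 5.2.1.2), so earlier progression has to be found by unscheduled assessment.
- Protocol 5.2.2 says the on-treatment biopsy is not done if the risk to the patient appears unacceptable.
- An early progressor biopsied on Day 57 or later stays in the window.

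The 80% is a planning expectation, not an observed rate, and the documents give no counterpart for placebo.

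**The case against.** The strongest reply is that the SAP never says these biopsies are excluded, and that its analysis text points to inclusion. Section 12.5.3.2 needs only a postbaseline result, which an early second biopsy is. The treatment policy strategy uses values after progression. The scheduled-time-point and listing rules most naturally govern by-visit tables, and the biomarker ANCOVA names no visit. The early biopsy is written into the protocol's schedule of assessments, so it is arguably scheduled. Where the SAP does set aside pre-Week 9 tumour data, it says so: 10.9.2 lists stable disease on an early unscheduled scan but leaves it out of the best-response summary. The third biopsy is limited to patients who already have a Week 9 sample, so for them the issue is only which sample to use.

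Most of this stands. A reader might infer that the SAP drops early progressors from the biomarker analyses. The documents do not support that as a statement of fact; it is one of two readings. The reply does not show that the plan is settled, however. The windowing rule names biopsies expressly and applies whatever the visit label. The inclusive reading resolves the early biopsy only by leaving the choice between second and third biopsies undefined.

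**Conclusion.** The point holds as an unresolved conflict within the SAP and with the protocol schedule, and it should be fixed. The SAP's windowing rule gives no analysis visit to a biopsy that the protocol makes mandatory, while its estimand and analysis sections imply that the biopsy counts. Bias follows only if the strict reading is the one programmed and early progression differs by arm.

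The number affected is unknown and probably small. About 3 of 25 setanaxib patients off treatment for any cause by Day 57 is a guide, resting on constant hazard and the protocol's own expectation.

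Two further inferences go too far:

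- A reader might apply an assumed median PFS to all 50 patients and count every early event as a lost biopsy. Such a count includes deaths, progression not seen until the Week 9 scan and patients not biopsied, and the shorter medians fit poorly with 80% of setanaxib patients being treated for 3 months.
- A reader might infer that the 90% power statement, which assumes at least 20 patients with paired samples, is undermined. That assumption concerns gene sequencing, which SAP 12.5.4.3 sends to a separate plan not available here.

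One limit applies: the SAP was written against protocol version 5.0, and version 4.0 is the one supplied. SAP 6.1 lists no departure on biopsy timing.

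**What to change.** In SAP 10.4 and 12.5.3.2, define the on-treatment biomarker value as the protocol's second biopsy, whatever its study day, and exclude the optional third (progression) biopsy from this endpoint. Sections 12.5.3.3 and 12.5.4.4 then follow by cross-reference. Show the Day 57 to 71 subset as a sensitivity analysis. The SAP already uses this anchor for PK, where the day of the second biopsy is a nominal time point (12.7).

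The cost is a few sentences of SAP text and one extra run, best settled before unblinding. The downside is slightly more variable time on drug at biopsy, which the sensitivity analysis addresses. The change removes only the exclusion that the window creates; patients who have no second biopsy remain missing.
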